## 2.3 BENEFIT/RISK ASSESSMENT

### COVID-19 Benefit-risk assessment

Dupilumab has shown clinical benefit in several type-2 driven immunological disorders, such as AD, asthma, and CRSwNP.

To date, more than 8000 participants have been treated with dupilumab during the clinical development program in several indications, of which AD, asthma, and CRSwNP are licensed in some countries.

Currently, there are insufficient data in participants with Coronavirus Disease-2019 (COVID-19) who are being treated with dupilumab. Thus, the safety and efficacy of dupilumab in COVID-19 patients are unknown. During the course of the clinical trial program, respiratory infections including viral infections were monitored and these events are not listed as adverse drug reactions (ADRs) with dupilumab.

The target population of EFC16723 is patients with uncontrolled, CRSsNP who have evidence of type-2 inflammation. These patients have failed medical therapies and/or surgical intervention and have active disease that causes significant impairment in function and quality of life. Therefore, these patients have a high unmet medical need for novel effective treatment. Participation in EFC16723 will provide an opportunity for these patients to be treated with a novel therapy that has proven efficacy in certain other disease states (ie, AD, asthma, and CRSwNP) where type-2 inflammation is the underlying driver of the disease process.

Based on the aforementioned potential benefits to patients participating in EFC16723, the Sponsor's assessment is that the benefit-risk remains favorable for patients to participate in this trial.

The Sponsor also recognizes that the COVID-19 pandemic may have an impact on the conduct of clinical trials. The Sponsor will monitor the situation closely and ensure the integrity of the trial conduct and data (see [Section 8](#)).

More detailed information about the known and expected benefits and risks and reasonably expected AEs of dupilumab is available in the IB.

#### 2.3.1 Risk assessment

No tissue targets or specific hazards to humans were identified in nonclinical general and reproductive toxicology studies.

Dupilumab has an extensive safety database. As of 28 March 2020, 10 191 participants were enrolled into the development program for dupilumab and included in the safety population: 382 as healthy volunteers, 4405 from AD studies, 3614 from asthma studies, 782 from CRSwNP studies, 232 from EoE studies, 103 from the grass allergy study, 145 from peanut allergy studies, 511 from the chronic obstructive pulmonary disease (COPD) study, 5 from prurigo nodularis (PN) studies, and 12 from the chronic spontaneous urticaria (CSU) study. The number of participants

exposed to dupilumab in clinical studies was 8720 (356 in healthy volunteer studies, 4052 in AD studies, 3263 in asthma studies, 470 in CRSwNP studies, 166 in EoE studies, 52 in the grass allergy study, 96 in peanut allergy studies, 256 in the COPD study, 3 in PN studies, and 6 in the CSU study. For the latest information, please refer to the current IB.

Based on the information retrieved from Intercontinental Marketing Services Health and using the World Health Organization's defined daily dose for dupilumab of 21.4 mg/day, the cumulative post marketing exposure to dupilumab is estimated to be 161 582 patient-years (01 January 2017 through 31 March 2020).

Dupilumab was generally well tolerated in all populations tested in clinical development programs consistent with a favorable benefit/risk profile. The adverse drug reactions (ADR) identified to date for dupilumab include injection site reactions, conjunctivitis (including allergic and bacterial), oral herpes, herpes simplex, blepharitis, keratitis, dry eye, eye pruritus, eosinophilia, serum sickness, anaphylactic reaction, angioedema, and arthralgia. These ADRs were generally mild or moderate, transient, and manageable. These ADRs were not observed consistently in all indications (see IB for greater details). More significant serious allergic reactions were very rare. Importantly, no increased overall infection risk was observed in patients treated with dupilumab.

Systemic hypersensitivity is established as an important identified risk with dupilumab. As protein therapeutics, all monoclonal antibodies are potentially immunogenic. Rare serious and systemic hypersensitivity reactions have been observed in the dupilumab program including serum sickness/serum sickness-like reaction in the adult AD program and anaphylaxis related to dupilumab in the adult asthma clinical trials.

The important potential risk for dupilumab is "eosinophilia associated with clinical symptoms in asthma patients." The observed increase in eosinophil count is transient, which is consistent with the current understanding of the mechanism of action of dupilumab. In dupilumab asthma studies, a small number of patients with asthma experienced serious systemic eosinophilia presenting with clinical features of eosinophilic pneumonia or vasculitis consistent with eosinophilic granulomatosis with polyangiitis, conditions which are often treated with systemic corticosteroid therapy. These events have been seen in other drug development programs for severe asthma and usually, but not always, have been associated with the reduction of oral corticosteroid therapy suggesting possible unmasking of these conditions with tapering of corticosteroids during dupilumab therapy. The association of dupilumab treatment and these events has not been established. Health care providers should be alert to eosinophilia associated with vasculitic rash, worsening of pulmonary symptoms, pulmonary infiltrate, cardiac complications, and/or neuropathy presenting in their patients, especially upon reduction of SCS.

Patients with known helminth infections were excluded from participation in clinical studies; therefore, it is not known if dupilumab will influence the immune response against helminth infections. Consequently, patients with pre-existing helminth infections should be treated for their helminth infection before initiating therapy with dupilumab.

The common ADR across all indications is injection site reactions. Other potential risks based on the safety profile in particular indications are discussed in the IB.

While long-term data are still accumulating, data from randomized, placebo-controlled trials and open-label extension studies to date have not identified any new safety concern in these populations. It is anticipated that dupilumab in patients with type-2 CRSsNP will have a favorable safety profile as observed across other type-2 driven immunological disorders.

### 2.3.2 Benefit assessment

Dupixent® (dupilumab) is authorized for marketing in over 60 countries worldwide including the US, European Union (EU) (Centralized Procedure), Japan, Canada, and Australia for the adult AD indication. Dupilumab is also authorized in the US, EU, and other jurisdictions for the adolescent AD indication, in the US for children 6 to 12 years old with AD, and in the US, EU, Japan, and other jurisdictions for the adult and adolescent asthma indication. Dupilumab also has approval for its CRSwNP indication in the US, EU, and Japan. For the latest information, please refer to the current IB.

There are no treatments specifically approved for CRSsNP in the US. Standard medical therapies, such as those based on EPOS 2020 guidelines, which include topical and oral corticosteroids, and antibiotics, do not provide adequate or lasting control of the symptoms in many patients with CRSsNP. A high unmet medical need exists for therapies that target underlying inflammatory processes in type-2 CRSsNP patients who are inadequately treated by the current standard of care.

Considering this unmet medical need and the known mechanism of action of dupilumab, the Sponsor is proposing to develop dupilumab for the treatment of type-2 CRSsNP for the following reasons:

1. There is a subset of CRSsNP patients with an underlying pathophysiology that is driven primarily by Type-2 inflammatory processes and is characterized by increased type-2 biomarkers such as blood eosinophils, type-2 comorbidities or recurrence after surgery. Dupilumab has demonstrated favorable safety and efficacy profiles across a broad range of diseases including AD, asthma, and CRSwNP where type-2 inflammation is a key driver of the underlying disease process.
2. Dupilumab has demonstrated significant efficacy in reducing sinus opacification, severity of CRS symptoms and nasal polyp burden in CRSwNP, a disease that shares several clinical and molecular features with CRSsNP with evidence of Type-2 inflammation.
3. A post-hoc analysis of the LIBERTY ASTHMA QUEST study demonstrated that dupilumab treatment improved sinonasal symptoms and health-related quality of life (HRQoL), as assessed by SNOT-22, in patients with CRS (20) and suppressed airway (FeNO) and systemic (total IgE, TARC) type-2 inflammatory biomarkers versus placebo (20). Furthermore, clinically meaningful improvement from baseline in SNOT-22 was observed primarily in patients who had peripheral blood eosinophil counts  $\geq 300$  cells/mm^3.

### **2.3.3 Overall benefit: risk conclusion**

Therefore, based on the totality of evidence to support the potential therapeutic benefit in CRSsNP, a patient population with an unmet medical need, the favorable benefit/risk profile across multiple indications, and the extensive safety database for dupilumab, the Sponsor is proposing to conduct a Phase 2 program with dupilumab for the treatment of CRSsNP with evidence of type-2 inflammation.

### 3 OBJECTIVES AND ENDPOINTS

**Table 1 - Objectives and endpoints**

Objectives	Endpoints
Primary	

 
• To evaluate the efficacy of dupilumab as assessed by the reduction at Week 24 in sinus opacification on computerized tomography (CT) scan in the dupilumab group only
 
	
 
• Change from baseline to Week 24 in opacification of sinuses assessed by CT scan using the Lund-Mackay (LMK) score in the dupilumab group
 

Secondary	

 
• To evaluate the efficacy of dupilumab as assessed by the reduction at Week 24 in sinus opacification on CT scan and sinus total symptom score (sTSS) compared to placebo
 
	
 
• Change from baseline to Week 24 in opacification of sinuses assessed by CT scan using the LMK score
 
• Change from baseline to Week 24 in sTSS*
 

 
• To evaluate the safety and tolerability of dupilumab in CRSsNP patients compared to placebo
 
	
 
• Incidence of treatment-emergent adverse events (TEAEs), of treatment-emergent serious AEs (TESAEs), and TEAEs leading to treatment discontinuation, abnormal laboratory values, and vital signs
 

 
• To evaluate the pharmacokinetics (PK) of dupilumab in CRSsNP patients compared to placebo
 
	
 
• Dupilumab concentration in serum
 

 
• Assessment of immunogenicity to dupilumab over time compared to placebo
 
	
 
• Assessment of immunogenicity to dupilumab as determined by the incidence, titer, and neutralizing antibody (NAb) status of treatment-emergent anti-drug antibody (ADA) response over time compared to placebo
 

Exploratory	

 
• [REDACTED]
 
	
 
• [REDACTED]
 

 
• [REDACTED]
 
	
 
• [REDACTED]
 

 
• [REDACTED]
 
	
 
• [REDACTED]
 

 
• [REDACTED]
 
	
 
• [REDACTED]
 


 
• [REDACTED]
 
	
 
• [REDACTED]
 

 
• [REDACTED]
 
	
 
• [REDACTED]
 

 
• [REDACTED]
 
	
 
• [REDACTED]
 

 
• [REDACTED]
 
	
 
• [REDACTED]
 

 
• [REDACTED]
 
	
 
• [REDACTED]
 

 
• [REDACTED]
 
	
 
• [REDACTED]
 

 
• [REDACTED]
 
	
 
• [REDACTED]
 

 
• [REDACTED]
 
	
 
• [REDACTED]
 

 
• [REDACTED]
 
	
 
• [REDACTED]
 

 
• [REDACTED]
 
	
 
• [REDACTED]
 

 
• [REDACTED]
 
	
 
• [REDACTED]
 

 
• [REDACTED]
 
	
 
• [REDACTED]
 

 
• [REDACTED]
 
	
 
• [REDACTED]
 

 
• [REDACTED]
 
	
 
• [REDACTED]
 

 
• [REDACTED]
 
	
 
• [REDACTED]
 

Objectives

Endpoints

-

### **3.1 APPROPRIATENESS OF MEASUREMENTS**

The primary efficacy assessment of change from baseline in the LMK CT scan score at Week 24 in the dupilumab group, will provide objective imaging-based measurement of benefit of CRSsNP patients. The LMK and a related total symptom score (TSS), as secondary endpoint with dupilumab group comparison to placebo, are 2 of the key assessments that have been successfully implemented and have provided clinically meaningful evidence of therapeutic benefit of dupilumab treatment after 24 weeks in the completed clinical development program of dupilumab in CRSwNP (19). The sTSS in this trial is a total score composed of three common, cardinal symptoms of CRSsNP, including nasal congestion, rhinorrhea (anterior/posterior), and facial pain/pressure that are daily assessed by the participant. This score will provide a comprehensive clinical assessment of the impact of dupilumab on the key symptoms of CRSsNP, and will complement the objective assessment provided by the well-validated LMK score. Other supportive assessments, including individual scores for the main symptoms in CRSsNP (NC/obstruction, loss of sense of smell, facial pain/pressure, and rhinorrhea) and visual analog scale (VAS) for rhinosinusitis severity will also be assessed. The SNOT-22 will also be collected to provide additional evidence of therapeutic benefit.

## 4 STUDY DESIGN

### 4.1 OVERALL DESIGN

This is a Phase 2 multicenter study to evaluate the efficacy and safety of dupilumab, in participants with uncontrolled CRSsNP. This is a randomized, double-blind, placebo-controlled study in adult participants regardless of screening eosinophil count to evaluate the treatment effect of dupilumab on sinus opacification as assessed by the LMK sinus CT scan total score and to provide data on safety.

All participants (adults only) will enter a screening period (2 to 4 weeks), with a 24 to 52-week treatment period, followed by post-treatment follow-up (12 weeks).

Approximately 70 adult participants will be randomized 1:1 (approximately 35 participants per arm) into 2 treatment groups as follows:

- Arm A: Dupilumab 300 mg q2w,
- Arm B: Matching placebo.

Randomization will be stratified by screening blood eosinophil count ( $\geq 300$  cells/mm $^3$  or  $< 300$  cells/mm $^3$ ), background INCS use (yes or no) and region.

To ensure enrollment according to the intended distribution of screening blood eosinophil count, alerts will be built into the IRT to control the number of participants in each stratification group as follows:

- $\geq 300$  cells/mm $^3$ : approximately 15 participants per arm,
- $< 300$  cells/mm $^3$ : approximately 20 participants per arm.

*Note: The treatment will stop for all participants when the LPI has completed 24 weeks of treatment. Therefore, all participants following Amendment 02 will be treated for at least 24 weeks and the other participants (enrolled before Amendment 02) will have variable treatment period and may continue up to 52 weeks.*

In addition, in order to have an adequate number of participants with comorbid asthma, alerts will be built into the IRT to limit the number of participants without comorbid asthma to no more than 70% of the randomized population.

During the study, participants who report deterioration requiring medical/surgical intervention may come to the site for clinical evaluation. An unscheduled visit may be used for this purpose and, if necessary, the Investigator may consider one of the treatment alternatives described in [Section 6](#).

### 4.2 SCIENTIFIC RATIONALE FOR STUDY DESIGN

EFC16723 is designed as a double-blind, randomized, placebo-controlled, study to minimize bias in data collection and interpretation. The presence of a placebo arm is appropriate for the objectives of this study since it will provide the most robust assessment of the efficacy and safety

of dupilumab. The study has a 24 to 52 -week study treatment period to provide initial evidence related to the treatment effect of dupilumab in patients with Type-2 inflammation (as indicated by peripheral blood eosinophil counts  $\geq 300$  cells/mm $^3$ ) CRSsNP and to provide safety information. In addition, a post-hoc analysis to assess the efficacy of dupilumab on upper airway symptoms as measured by SNOT-22 in the subset of asthma patients with CRS from the dupilumab Phase 3 asthma study EFC13579 (QUEST) was performed. Clinically meaningful improvement from baseline in SNOT-22 was observed only in patients who had peripheral blood eosinophil counts  $\geq 300$  cells/mm $^3$  and not in those with  $< 300$  cells/mm $^3$ . In the study, to further evaluate the predictive value of baseline peripheral blood eosinophil counts as a potential marker of treatment response to dupilumab, a subset of participants with blood eosinophil counts of  $< 300$  cells/mm $^3$  will be randomized while the primary analysis population will remain as participants who have peripheral blood eosinophil counts  $\geq 300$  cells/mm $^3$ .

The 24-week treatment duration should be sufficient for the demonstration of the efficacy with dupilumab based on the efficacy results seen in CRSwNP. This duration is also sufficient for safety assessment given the extensive safety experience with dupilumab including in the related condition of CRSwNP.

Rescue medications and/or surgery for CRSsNP deemed necessary by Investigators will be allowed, which mirror the expected future therapeutic paradigm of dupilumab in this population in clinical practice.

The primary efficacy assessment will be change from baseline in the LMK at Week 24 in the dupilumab group. Other supportive assessments, including sTSS scores for the main symptoms in CRSsNP (nasal congestion [NC]/obstruction, loss of sense of smell, rhinorrhea, facial pain/pressure), VAS for rhinosinusitis severity, and SNOT-22 will also be collected, to provide additional evidence of therapeutic benefit.

Changes in the LMK and sTSS, as secondary endpoint, will provide both objective imaging measure of benefit and evidence of symptomatic improvement in the cardinal clinical manifestations of CRSsNP patients, respectively other secondary and exploratory measures, including individual scores for the main symptoms in CRSsNP, VAS for rhinosinusitis severity, and SNOT-22, that assess other disease manifestations of CRSsNP and the associated impact on the quality of life in participants.

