### 9.2 SAMPLE SIZE DETERMINATION

Sample size calculation was performed to ensure reasonable accuracy for the estimation of the primary endpoint in participants treated with dupilumab with screening blood eosinophil count  $\geq 300$  cells/mm $^3$ . With a 1:1 randomization ratio, a standard deviation (SD) of 5 and a dropout rate of 10%, a sample size of approximately 30 participants with screening blood eosinophil count  $\geq 300$  cells/mm $^3$  will provide a half-width of approximately less than 3 for the 2-sided 95% CI in the dupilumab group which is deemed reasonable.

In addition, it is planned to include approximately 40 participants with screening blood eosinophil count  $< 300$  cells/mm $^3$ . Thus, the planned total sample size is approximately 35 participants per arm.

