### 3.3.2 Main analytical approach

Change from baseline to Week 24 in LMK score and in sTSS comparing dupilumab to placebo will be analyzed on the ITT with screening blood eosinophil count  $\geq 300$  cells/mm^3 population. Handling of IEs will follow that of the primary endpoint. Otherwise, no missing data will be imputed. Descriptive statistics will be provided by intervention group. Mean treatment difference (dupilumab vs placebo) and the corresponding 95% CI (based on the t distribution) will be provided.

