### 3.4.2 Main analytical approach

Change from baseline to Week 24 endpoints and PGIC at Week 24 will be analyzed on the ITT with screening blood eosinophil count  $\geq 300$  cells/mm^3 population comparing dupilumab to placebo except for the following:

- Change from baseline to Week 24 in FEV1 and in ACQ-6 will be analyzed on the ITT with screening blood eosinophil count  $\geq 300$  cells/mm^3 and with comorbid asthma subgroup in the dupilumab group.
- Change from baseline to Week 24 in LMK and in sTSS will be analyzed on the ITT population (regardless of blood eosinophil count) in the dupilumab group.

Handling of IEs will follow that of the primary endpoint. Otherwise, no missing data will be imputed. Descriptive statistics will be provided by intervention group. For endpoints comparing dupilumab to placebo, treatment difference (dupilumab vs placebo) and the corresponding 95% CI will be provided. For endpoints analyzed in the dupilumab group, 95% CI in the dupilumab group will be provided. The 95% CI will be constructed based on the t distribution.

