### 3.4.3 Exploratory analyses on the [REDACTED] [REDACTED]

Change from baseline to Week 24 in [REDACTED] comparing dupilumab to placebo will be analyzed using the same approach as the secondary endpoints on the [REDACTED] populations.

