## 4 SAMPLE SIZE DETERMINATION

Sample size calculation was performed to ensure reasonable accuracy for the estimation of the primary endpoint in participants treated with dupilumab with screening blood eosinophil count  $\geq 300$  cells/mm $^3$ . With a 1:1 randomization ratio, a standard deviation (SD) of 5 and a dropout rate of 10%, a sample size of approximately 30 participants (15 per arm) with screening blood eosinophil count  $\geq 300$  cells/mm $^3$  will provide a half-width of approximately less than 3 for the 2-sided 95% CI in the dupilumab group which is deemed reasonable.

In addition, it is planned to include approximately 40 participants (20 per arm) with screening blood eosinophil count  $< 300$  cells/mm $^3$ . Thus, the planned total sample size is approximately 35 participants per arm.

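### Eosinophils are to be evaluated as a predictive marker, but no legible analysis estimates the difference between the treatment effects at or above and below 300 cells/mm³

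*Protocol*

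**What the plan says.** Protocol 4.2 gives the reason for randomising a subset below 300 cells/mm³: "to further evaluate the predictive value of baseline peripheral blood eosinophil counts as a potential marker of treatment response to dupilumab". Randomisation is stratified at that cut-off (Protocol 4.1 and 6.3). SAP 4 sets the group sizes: "a sample size of approximately 30 participants (15 per arm) with screening blood eosinophil count" at or above 300, and for the rest "it is planned to include approximately 40 participants (20 per arm) with screening blood eosinophil count" below 300. SAP Table 3 defines an ITT population for each group.

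The legible efficacy analyses are:

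- **Primary (SAP 3.2.2):** LMK change at Week 24 in the dupilumab arm of the ≥300 population.
- **Secondary (SAP 3.3.2):** LMK and sTSS against placebo, in the ≥300 population only: "Mean treatment difference (dupilumab vs placebo) and the corresponding 95% CI (based on the t distribution) will be provided".
- **Exploratory (SAP 3.4.2):** most endpoints in the ≥300 population; FEV1 and ACQ-6 in its asthma subgroup, dupilumab arm only; and LMK and sTSS again, which "will be analyzed on the ITT population (regardless of blood eosinophil count) in the dupilumab group".
- **Exploratory (SAP 3.4.3):** endpoint and populations redacted, method readable: "comparing dupilumab to placebo will be analyzed using the same approach as the secondary endpoints".

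Amendment 02 removed the model-based and subgroup analyses (SAP Table 7). Protocol 9.1 states that no hypotheses will be tested.

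**The concern.** To judge whether a baseline measurement predicts response to a drug, one has to ask whether the drug–placebo difference changes with that measurement. Here that is one difference minus another, with its own standard error. A plan that stops at one interval per population leaves readers to compare the intervals by eye, and the natural comparison is whether each one excludes zero. That comparison is unreliable, because two modest samples from populations with the same true effect will often fall on opposite sides of the line.

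The temptation is a practical one. Protocol 4.2 supports the 300 cut-off with a post-hoc finding from the sponsor's asthma study, in which meaningful SNOT-22 improvement from baseline appeared above the cut-off and not below it. Reading the present results the same way could support a marker that has no predictive value, or dismiss one that has.

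**Working it through.** **Inputs**

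- Planned participants per arm: 15 at ≥300 and 20 at <300 (SAP 4).
- Allocation, SD and dropout (Protocol 9.2): "With a 1:1 randomization ratio, a standard deviation (SD) of 5 and a dropout rate of 10" per cent. The SD of 5 is given for LMK change in the ≥300 dupilumab group. Using it for the placebo arm and for the <300 group is my assumption, so I also show SD 4 and 6.
- After 10% dropout: 15 × 0.9 = 13.5 and 20 × 0.9 = 18 per arm.
- The true effects used in step 4 are assumptions. The documents give none.

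**1. The plan's own figure.** Protocol 9.2 says the ≥300 sample "will provide a half-width of approximately less than 3 for the 2-sided 95% CI in the dupilumab group which is deemed reasonable".

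Half-width = t(0.975, n−1) × SD/√n. At n = 13.5 this is 2.169 × 5/√13.5 = 2.95. Whole numbers give 3.02 at n = 13 and 2.89 at n = 14. The stated figure is reproduced.

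**2. The dupilumab–placebo difference within each population.** SE = SD × √(2/n).

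- ≥300: SE = 5 × √(2/13.5) = 1.92. Half-width = t(25) × SE = 2.060 × 1.92 = 3.96.
- <300: SE = 5 × √(2/18) = 1.67. Half-width = t(34) × SE = 2.032 × 1.67 = 3.39.

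**3. The contrast between the two differences.** SE = SD × √(2/13.5 + 2/18) = 5 × 0.509 = 2.55, with 2 × 13.5 + 2 × 18 − 4 = 59 degrees of freedom.

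| SD in all four cells | SE | 95% half-width, LMK points |
|---|---|---|
| 4 | 2.04 | 4.1 |
| 5 | 2.55 | 5.1 |
| 6 | 3.06 | 6.1 |

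With no dropout and SD 5 the half-width is 4.8.

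**4. How often separate intervals mislead when the effects are equal.** Let p_H and p_L be the chances that the ≥300 and <300 intervals exclude zero in the beneficial direction. Both come from the noncentral t distribution with the step 2 standard errors. The populations are independent, so the chance that exactly one excludes zero is p_H(1 − p_L) + p_L(1 − p_H).

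| Same true effect in both groups | p_H | p_L | Exactly one excludes zero | Only the ≥300 interval does |
|---|---|---|---|---|
| 1 | 0.07 | 0.08 | 14% | 7% |
| 2 | 0.17 | 0.21 | 31% | 13% |
| 3 | 0.32 | 0.42 | 47% | 19% |
| 4 | 0.52 | 0.65 | 50% | 18% |
| 5 | 0.70 | 0.83 | 37% | 12% |
| 6 | 0.85 | 0.94 | 19% | 5% |

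The pattern that would flatter the marker, with only the ≥300 interval excluding zero, is the smaller share. The opposite pattern is likelier because the <300 group is larger. Either one misreads equal effects.

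**5. sTSS.** Neither document gives an SD for sTSS, so the precision of that contrast cannot be stated.

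**The case against.** **Redaction.** The exploratory objectives are blacked out in both documents, as are the endpoint and populations of SAP 3.4.3, and SAP 3.4 sends some exploratory work to separate documents. A reader might infer that the sponsor never planned the contrast. The documents do not support that, because it could sit in hidden text. What stands is narrower: the readable method of 3.4.3 is the within-population one, and no other visible passage supplies the contrast.

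**No test was intended.** A reader might infer that the low-eosinophil group was recruited to test an interaction. The protocol speaks of evaluating a potential marker, tests no hypotheses, and in its amendment 02 rationale calls the low-eosinophil group existing. Its size therefore partly reflects earlier enrolment. This is right, and it means the gap is a missing estimate, not a missing or underpowered test.

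**No such decision rule is written.** Nothing in the plan says that predictive value will be judged by which interval excludes zero. That is correct. Step 4 describes a risk in reporting, not a planned analysis, and it is greatest for mid-sized effects.

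**Readers can subtract.** If 3.4.3 does report the <300 difference, which is an inference from Table 3 and from its reference to more than one population, the contrast can be worked out by hand. This makes the fix cheap. It does not commit the sponsor to rest its statement on the contrast.

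**The single-arm ITT analysis.** A reader might add that showing ITT LMK and sTSS in the dupilumab arm alone is part of the same fault. It is a separate question: a pooled result, with or without placebo, says nothing about prediction, and 3.4.3 may already give the placebo comparison.

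**Conclusion.** The point holds for the visible text. Protocol 4.2 states a predictive question, and the legible SAP analyses answer only within-population ones. The LMK contrast would have a half-width of about 5.1 points on a 0–24 scale, against the 3 points that Protocol 9.2 calls reasonable for the primary estimate. It is therefore exploratory, and only a large difference between the groups could be distinguished from none. The 31–50% disagreement rate depends on SD 5 in all four cells and on an equal true effect of 2 to 5 points, and it should not be quoted without those conditions. The primary and secondary results are unaffected.

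**What to change.** In SAP 3.4, unless the redacted text already does so:

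- Add, labelled exploratory, the ≥300 minus <300 difference in the dupilumab–placebo effect on Week 24 LMK and on Week 24 sTSS, each with a t-based 95% CI and the same handling of intercurrent events as the primary endpoint.
- State that any comment on eosinophils as a predictive marker will rest on this contrast, and not on whether the separate intervals include zero.

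The cost is two rows from data already being collected, in strata already used for randomisation. The drawback is a wide interval, which will limit what can be claimed about the marker.
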